Thoracic epidural analgesia (TEA) has been a key part of opioid-sparing multimodal perioperative analgesia since ERAS was introduced over a decade ago in Europe. Many randomized controlled trials have focused on the benefits of TEA, which have demonstrated that TEAs are effective in attenuating the surgical stress response and reducing pain and opioid consumption for up to 72 hours (h) following abdominal incisions. TEA also has an impact on complications following abdominal surgery, reducing the time to bowel recovery by up to 36 h and may reduce cardiac and respiratory complications in high-risk patients.⁶⁻⁸ While analgesia and recovery seem to be better with TEA than intravenous opioid patient controlled analgesia (PCA), the value of TEA compared to other loco-regional nerve blocks for patients on ERAS programs following open gynecologic surgery is unknown. TEA failure rates are as high as 30% and many of these patients will require supplemental opiates.⁹ TEA is also expensive.

Given these disadvantages, some leading ERAS programs use surgical site infiltration with long acting local anesthetics in lieu of TEA. Extended-release liposomal bupivacaine (LB) was recently approved by the FDA for single-dose surgical site infiltration to produce postsurgical analgesia. Cost and concerns for reimbursement for LB have hindered approval of LB within pharmacy formularies. However the cost of TEA exceeds that of LB. The cost of one 20mL single vial use of LB is less than or equal to the cost of a continuous epidural kit and does not incur the additional costs of TEA: 1) professional fees for placement and daily management and 2) use of operating room time for placement, which is estimated at \$14 per minute at our institution. To date, there has never been a comparison between the analgesic efficacy of TEA and LB surgical site infiltration following open abdominal surgery.

Hypothesis: The goal of this project is to test the hypothesis that surgical site infiltration with LB is non-inferior to and more cost effective than TEA for patients undergoing open gynecologic surgery on an established ERAS program using a non-inferiority randomized trial design. The impact of TEA and

surgical site infiltration with LB on neuroendocrine and inflammatory mediators of the surgical stress response (SSR) will also be investigated as a translational endpoint.

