Importance of Research: This study would be the first randomized trial comparing the value of the two prevailing modalities of loco-regional analgesia (TEA and LB surgical site infiltration) used by ERAS programs for open abdominal surgery in the U.S. The proposed value analysis is unique in accounting for a wide spectrum of quality, outcome and cost variables. Further, it has potential to set a precedent for quantifying the impact of discrete ERAS components on the surgical stress response. While the concept and theory behind surgical stress are old, little is known about its pathophysiology in the era of modern surgery. Results from this study would also better define the optimal non-opioid pain management regimen for patients recovering from open abdominal surgery and are urgently needed by the American College of Surgeons (ACS) and the Society of Gynecologic Oncology (SGO) in formulating our national ERAS guidelines as well as strategies for opioid reduction.

2. Objectives (include all primary and secondary objectives)

Primary objectives:

To test the hypothesis that surgical site infiltration with liposomal bupivacaine (LB) is non-inferior to thoracic epidural analgesia (TEA) using the coprimary efficacy endpoints: (1) the mean Area under the Curve (AUC) of visual analog scale (VAS) pain intensity scores from 0 to 48 hours postoperatively and (2) total opioid consumption (IV morphine equivalents, mg) from 0 to 48 hours postoperatively.

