5. Length of hospital stay and time (in days) to meeting discharge criteria. Often, patients remain inpatient beyond the time at which they first meet discharge criteria due to a variety of psychosocial factors. Thus, length of hospital stay and time (in days) to meeting discharge criteria will be separately recorded. Discharge eligible criteria include: (1) hemodynamically stable, (2) afebrile, (3) ROBF, (4) pain controlled with oral analgesics, (5) independence with ADLs, (6) walking greater than 250 feet.

6. Total intravenous fluids administered and time to postoperative diuresis defined as the time lapse from date of surgery (DOS) to a net negative fluid balance sustained over a 24 h time period.

7. Need for vasopressors (amount and duration).

8. Incidence of major postoperative complications, including 30-day hospital readmission.

9. Total direct costs associated with loco-regional anesthesia: The analysis will include the direct variable cost of supplies and pharmacy (including initiation of PCA in the event of block failure) as well as anesthesia professional fees (TEA only; both intraop and postop) and cost of OR time in minutes to perform the blocks.

10. Post-discharge narcotic utilization. Total outpatient narcotic use during the immediate outpatient postoperative period will be obtained from the patient by nurse phone survey on postoperative day 14, provided the patient is outpatient and not still admitted or readmitted to the hospital.

Translational Endpoints:

1. Biomarkers of surgical stress response. Blood samples (10mL of whole blood) will be collected on the DOS when routine IV access is established in preop or the operating room and postoperative days 1 through postoperative day 7 coinciding with routine IV access for blood, for analysis of peripheral blood counts. Blood collection on postoperative day 0 is optional. Serum will

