Many randomized controlled trials over the past 20 years have focused on the benefits of TEA. TEA is effective in attenuating the surgical stress response and reducing pain and opioid consumption for up to 72 hours (h) following abdominal incisions, and also has an impact on complications following abdominal surgery, reducing the time to bowel recovery by up to 36 h and may reduce cardiac and respiratory complications in high-risk patients.⁶⁻⁸ While analgesia and recovery seem to be better with TEA than intravenous opioid patient controlled analgesia (PCA), the role of TEA in pain control for patients on ERAS programs following open gynecologic and colorectal surgery is controversial. TEA failure rates are as high as 30% and many of these patients will require supplemental opiates.⁹ The sympathetic block that results from TEA commonly results in hypotension that results in at least temporary discontinuation of the infusion, prompts intravenous fluid administration to already volume overloaded patients and may require treatment with vasopressors.¹¹ TEA may hinder achievement of other ERAS goals such as mobilization and removal of urinary catheters, and TEA has been shown to increase length of hospital stay and complication rates in gynecologic cancer surgery.^{12, 13}

Given these disadvantages, some leading ERAS programs use surgical site infiltration with long acting local anesthetics in lieu of TEA. Extended-release liposomal bupivacaine (LB) was recently approved by the FDA for single-dose surgical site infiltration to produce postsurgical analgesia. The liposomal preparation consists of microscopic multi-vesicles with a lipid-soluble lining and an aqueous core containing encapsulated bupivacaine allowing it to be slowly released over a period of up to 72–96 h.¹⁴ Existing data indicate that surgical site infiltration with LB following mastoplasty and open colectomy decreases postoperative opioid requirements and length of stay.^{15, 16} Recently, the Mayo Clinic published their

experience with abdominal incision injection of LB versus standard bupivacaine hydrochloride after laparotomy for gynecologic malignancies. Compared to bupivacaine hydrochloride, abdominal incision infiltration with LB was associated with less opioid consumption as well as lower rates of postoperative nausea and ileus. Pain scores, length of hospital stay and total pharmacy costs did not differ between the groups.¹⁷

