To date, there has never been a comparison between the analgesic efficacy of TEA and LB surgical site infiltration following open abdominal surgery. In many cases, cost and concerns about reimbursement have hindered approval of LB within hospital formularies. These concerns stem from Centers for Medicare and Medicaid Services (CMS) mandated bundling of reimbursement for all drugs used during a surgical procedure with the procedure itself as well as from inconsistencies in contracts between hospitals and private/commercial insurers regarding payment policies for separately payable drugs. However, the cost of TEA significantly exceeds that of LB. The cost of a 20 mL single use vial of LB is less than or equal to the cost of a continuous epidural kit. TEA incurs the added expenses of (a) professional fees for placement and daily management and (b) the use of operating room (OR) time for placement (~\$14 dollars/min at our institution). Currently on the JHH gynecologic oncology ERAS program, 40% of epidurals are placed in the OR with an average OR time expenditure of 30 minutes per epidural. Additional pharmacy costs also accumulate in the 30% of cases of failed TEA.

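### The hypothesis says LB is more cost effective than TEA, but the only cost endpoint covers block-related direct costs and no cost-effectiveness analysis is planned

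*Combined protocol and SAP*

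**What the plan says.** The hypothesis has two halves. Both the opening Hypothesis paragraph and the last paragraph of section 3 (Background) describe liposomal bupivacaine (LB) infiltration as "non-inferior to and more cost effective than TEA for patients undergoing open gynecologic surgery", where TEA is thoracic epidural analgesia. Importance of Research adds that "The proposed value analysis is unique in accounting for a wide spectrum of quality, outcome and cost variables", and the Benefits section repeats this.

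Cost is measured once, in item 9 of the secondary objectives (section 2): "Total direct costs associated with loco-regional anesthesia: The analysis will include the direct variable cost of supplies and pharmacy". The definition goes on to add "including initiation of PCA in the event of block failure) as well as anesthesia professional fees (TEA only; both intraop and postop" and finally the "cost of OR time in minutes to perform the blocks".

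Items 5 to 8 of the same list record hospital stay, intravenous fluids, vasopressors, major complications and 30-day readmission. None of them enters item 9.

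Section 7, under secondary outcome variables, assigns a Poisson model to length of stay, log-rank tests to bowel function and diuresis, and chi-square tests to complications. It does not mention cost.

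**The concern.** A cost-effectiveness claim sets the cost that follows from choosing one treatment over another against its effect. Item 9 stops at the cost of delivering the block and of starting PCA when the block fails. It is not paired with an effect, and the plan gives no perspective, time horizon or decision rule for cost.

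The resources left out are ones the protocol itself expects to differ. The Background says that hypotension under TEA "prompts intravenous fluid administration to already volume overloaded patients and may require treatment with vasopressors", and it cites evidence that TEA lengthens stay and raises complication rates in gynecologic cancer surgery.

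As written, the trial could report a lower block cost for LB and describe it as more cost effective, whatever happened to stay or readmission. It could equally miss a saving if TEA does lengthen stay. In both cases the second half of the hypothesis goes untested, in a trial that presents its results as input to national guidelines.

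**Working it through.** The plan states no expected cost difference, and no sample size or precision for cost, so it has no cost result of its own to reproduce. The check compares the claim with the endpoint and then puts one item to scale.

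**1. What is costed, and what is only recorded**

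| Resource | In item 9 | Recorded elsewhere | Background expects TEA to affect it |
|---|---|---|---|
| Block supplies and pharmacy | yes | – | – |
| PCA after block failure | yes | – | – |
| Professional fees | yes, TEA only | – | – |
| OR minutes for the block | yes | – | – |
| Hospital stay | no | item 5 | yes |
| Intravenous fluids | no | item 6 | yes |
| Vasopressors | no | item 7 | yes |
| Major complications | no | item 8 | yes |
| 30-day readmission | no | item 8, incidence only | not stated |

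**2. What is analysed.** Section 7 contains no cost model, cost-effectiveness ratio or net benefit. The promised value analysis is not defined anywhere.

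**3. What is asserted in advance.** The Background already says "the cost of TEA significantly exceeds that of LB". Its reasons are that the LB vial costs no more than the epidural kit, that TEA carries professional fees and OR time, and that failed epidurals add pharmacy cost. These are largely the components of item 9. The size of the difference still depends partly on patient-level PCA use, fees and OR minutes.

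**4. Scale of one counted item.** Inputs from the Background: 40% of epidurals are placed in the OR, each takes 30 minutes on average, and OR time costs about 14 dollars per minute.

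- Per epidural placed in the OR: 30 × 14 = 420 dollars.
- Average per TEA patient: 0.40 × 420 = 168 dollars.

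The documents give no price for a hospital day. For an assumed price *c*, the difference in mean stay that equals this item is 168 / *c*:

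| Assumed dollars per day | Days equal to 168 dollars |
|---|---|
| 500 | 0.34 |
| 1,000 | 0.17 |
| 2,000 | 0.08 |
| 3,000 | 0.06 |

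**5. What cannot be computed.** The documents give no dollar figure for the kit, the professional fees, PCA or infiltration minutes. For LB, the Costs section budgets 40,000 dollars for drug plus pharmacy, or 40,000 / 50 = 800 dollars per patient if it covers 50 LB patients only. The net block-cost difference cannot be derived from these figures.

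**The case against.** The strongest defence is that item 9 is labelled accurately and measures the items on which the protocol rests its own cost argument. Cost-effectiveness is absent from the formal primary objective, and no decision rule or sample size depends on it. Stay and complications would be reported beside block cost, so a bad result on either would be visible. With non-inferior efficacy, the comparison could be read as cost-minimisation. Looking only at block cost is also a legitimate perspective, because stay is partly driven by psychosocial factors, as item 5 acknowledges.

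Part of this stands. The endpoint is sound for what it measures, and the issue is secondary. But reporting stay and complications side by side does not test the cost-effectiveness half of the hypothesis. The plan does not propose a cost-minimisation reading, and non-inferiority on 48-hour pain and opioid use does not make stay, complications or readmission equal, so their costs cannot be assumed to cancel. If the general sentence in section 7 on t-tests or Mann-Whitney tests is meant to cover cost, skewed costs would go to Mann-Whitney, which does not compare mean cost.

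Three stronger readings are tempting, and the documents do not support them:

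- *The cost result merely restates a price list.* PCA after failure, OR minutes and postoperative fees vary by patient.
- *The Background says TEA costs more through stay, fluids and vasopressors.* It presents these as clinical consequences. Its cost argument rests on the kit, fees, OR time and pharmacy.
- *Counting stay would reverse the cost result.* The break-even in days offsets one component only, and the other prices are not given.

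**Conclusion.** The concern holds in this form: the plan states a cost-effectiveness hypothesis and promises a value analysis, but it measures block-related direct cost only and specifies no cost analysis. Item 9 can show whether the block and its immediate rescue cost less with LB. It cannot show that LB is more cost effective.

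Only an indication of size is possible. A difference of 0.06 to 0.34 days in mean stay is worth as much as the 168-dollar OR-time item. This assumes 500 to 3,000 dollars per hospital day, and the protocol's current 40% and 30-minute figures. An uncosted difference of that order is therefore comparable to an item the plan chose to count. Nothing here shows which way total cost would go.

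The change is worth making because it alters what the trial may conclude about cost. The co-primary tests, their margins and the sample size are unaffected.

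**What to change.** Either of two changes resolves the mismatch.

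**Option A: add a total cost.** Keep block cost as a reported component. Pre-specify a total perioperative cost per patient by applying one fixed unit-cost table to recorded resources: block, PCA, OR minutes, fluids, vasopressors and index hospital days. Add a unit cost per 30-day readmission, since only incidence is recorded. State the perspective and time horizon, and how readmissions after day 14 are captured, because patients count as on study only to that day. Compare mean cost by arm with a bootstrap interval, and report it beside the co-primary effect results. Say in section 7 that this pairing is what the plan means by cost effective; a cost difference alone would not carry the claim.

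The price is the work of building the unit-cost table, some protocol and SAP wording, and a wider interval, because total cost varies more than block cost.

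**Option B: narrow the claim.** Restrict the hypothesis, in the opening paragraph and at the end of the Background, to *lower direct cost of loco-regional anesthesia*. Remove the cost-effectiveness and value-analysis claims from Importance of Research and Benefits. This costs wording only, but the trial then gives up the broader conclusion.

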Coprimary efficacy endpoints will be used to test the hypothesis that surgical site infiltration with LB is non-inferior to TEA: (1) the mean Area under the Curve (AUC) of visual analog scale (VAS) pain intensity scores from 0 to 48 hours postoperatively and (2) total opioid consumption (IV morphine equivalents, mg) from 0 to 48 hours postoperatively will be compared between the two treatment groups. The mean AUC of VAS pain intensity scores endpoint incorporates the use of rescue medications by using an imputation method called windowed worst observation carried forward (WWOCF). This method imputes a subject's pain score as their worst pain score for a pre-specified window after a rescue medicine. Subjects will be evaluated for pain intensity at rest at 6, 12, 18, 24, 30, 36, 42, 48, and 72 hours after surgery and then once daily (at noon \pm 4 hours) through postoperative day 14. Subjects will also record an unscheduled pain score immediately before any requested opioid pain medication. The exact time of the assessment will be recorded to limit variability. Total opioid consumption in IV morphine equivalents (mg) during the first 48 hours postoperatively will be tracked for each subject.

Secondary objectives:

To compare the impact of TEA and surgical site infiltration with LB on patient reported and clinical outcomes as well as on neuroendocrine and inflammatory mediators of the surgical stress response using the following measures:

1. Mean patient-perceived quality of recovery score on postoperative days 1-7 (QoR-15).
2. Time to return of bowel function (ROBF) and incidence of postoperative ileus.
3. Mobility Level.
4. Degree of sedation.
5. Length of hospital stay and time (in days) to meeting discharge criteria.
6. Total intravenous fluids administered and time to postoperative diuresis.
7. Need for vasopressors (amount and duration).
8. Incidence of major postoperative complications, including 30-day hospital readmission.

9. Total direct costs associated with loco-regional anesthesia.
10. Post-discharge narcotic utilization.

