All participants will otherwise be enrolled on the standard gyn-oncology ERAS pathway which includes pre-operative education, pre-operative medications, post-operative medications, post-operative fluid management, and mobility and feeding protocols.

Participation will be offered to patients undergoing a planned laparotomy via midline vertical skin incision on the gynecologic oncology service. Patients will be identified from gynecologic oncology pre-operative clinics. Eligible participants will be stratified based on pre-operative likelihood of malignancy (into likely benign disease vs. likely malignant disease). This stratification will be based upon the surgeon's preoperative impression of likelihood of malignancy. Participants will then be randomized 1:1 via a stratified randomized technique that accounts for a binary (yes/no) likelihood of malignancy by the inpatient pharmacy within 48 hours of surgery to the two study arms. Consent for study participation will be reviewed with the patient and signed prior to surgery.

In the rare event a patient enrolled on trial does not proceed with surgery, their slot will not be reallocated in the randomization scheme. Specifically, the inpatient pharmacy will generate random treatment assignments as follows:

1. IDS has randomization list from statistician
2. Randomization is stratified by "suspicion of cancer – Yes or No"
3. Study team will complete Randomization Request form prior to date of surgery and fax to IDS
4. If randomized to liposomal bupivacaine arm,
 - a. The authorized prescriber will enter Epic order (which will be modified to reflect the new IRB number)
 - b. At time of surgery an OR staff member will call IDS to coordinate pickup/delivery of study drug
5. If randomized to TEA arm,
 - a. The study team will notify the anesthesia block team the day before surgery to put the patient on the block list as per existing clinical work-flow for patients planned for pre-procedure blocks.

All participants will be enrolled on the standard gyn-oncology ERAS pathway which includes pre-operative education, pre-operative medications, post-operative medications, post-operative fluid management, and mobility and feeding protocols.

Patients will be considered to be “on study” until collection of VAS pain scores and opioid consumption is complete on postoperative day 14. Each participating individual will have no extra or additional outpatient study visits.

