Intention to treat statistical analyses will be used to test the null hypothesis. Thus, if a patient has been randomized to the TEA arm of the trial and an epidural cannot be placed or cannot be used due to other circumstances (ie. persistent hypotension) the patient will receive the other elements of the ERAS multimodal pain bundle, which is consistent with our current clinical practice and that patient's data will be included in the dataset for the TEA arm in the final analysis. Additionally, in the event a participant wishes to drop out of the study prematurely postoperatively (ie. declines further blood/saliva collection and/or to fill out surveys), they will be allowed to do so and the data collected during their enrollment period will still be included in the dataset for their respective treatment arm unless they submit a formal written objection.

Secondary outcome variables:

T-tests or the nonparametric Mann-Whitney test will be used to compare normally and non-normally distributed data between the study arms. The log-rank test will be used to compare the time to (ROBF) as well as the time to postoperative diuresis to account for right censoring in which case no event (ROBF/diuresis) is observed within the observed time. A Poisson regression model will be used to compare the length of hospital stay. Chi-square tests will be used to compare the incidence of major postoperative complications between the two treatments. Chi-square tests will also be used to compare the incidence of major postoperative complications between the two treatments. Daily mean and median as well as mean baseline change in surgical stress biomarkers will be compared between treatment groups using t-tests or the Mann-Whitney test depending on whether data are normally or non-normally distributed. Average daily QoR-15 scores will be compared between the study cohorts.

b. Early stopping rules.

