CRFs will be organized in a binder for each patient participant. The binder will follow the patient with their inpatient chart throughout their perioperative journey. At the time of hospital discharge, the each CRF binder will be stored in a locked filing cabinet in the PI's office. Post-operative pain medication logs collected from patients in the outpatient setting at their first postoperative appointment will be given to the PI to file with the other CRFs in the patient's binder. All patient data will then be entered into a secure, password protected REDCap database housed on a JHED-enabled computer and only those listed as investigators on this study will have access to this database to minimize the risk of breaches of confidentiality.

- e. Financial risks to the participants.

There is no anticipated financial risk to the participants. Liposomal bupivacaine and surgical stress biomarker assays will be paid for by the study and will not be a cost to the individuals participating. There is no anticipated burden of extra cost to patients beyond what industry funding and standard perioperative care provide.

2. Benefits

- a. Description of the probable benefits for the participant and for society.

This study would be the first randomized trial comparing the value of the two prevailing modalities of loco-regional analgesia (TEA and LB surgical site infiltration) used by ERAS programs for open abdominal surgery in the U.S. The proposed value analysis is unique in accounting for a wide spectrum of quality, outcome and cost variables. Further, it has potential to set a precedent for quantifying the impact of discrete ERAS components on the surgical stress response. While the concept and theory behind surgical stress are old, little is known about its pathophysiology in the era of modern surgery. Results from this study would also better define the optimal non-opioid pain management regimen for patients recovering from

open abdominal surgery and are urgently needed by the American College of Surgeons and the Society of Gynecologic Oncology in formulating our national ERAS guidelines.

3. Payment and Remuneration

- a. Detail compensation for participants including possible total compensation, proposed bonus, and any proposed reductions or penalties for not completing the protocol.

Patients will be not be given any payment or compensation for participating in this study.

4. Costs

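### Post-discharge opioid use is recorded only for patients out of hospital on postoperative day 14, so readmitted patients lose a value for opioids already taken at home

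*Combined protocol and SAP*

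**What the plan says.** The list of secondary measures in Section 2 names the endpoint only as "Post-discharge narcotic utilization", without a unit or a window. The description of item 10 later in that section supplies the method: "Total outpatient narcotic use during the immediate outpatient postoperative period will be obtained from the patient by nurse phone survey on postoperative day 14". It then limits who is asked: "provided the patient is outpatient and not still admitted or readmitted to the hospital".

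Three other places bear on it.

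- Section 4a keeps patients on study "until collection of VAS pain scores and opioid consumption is complete on postoperative day 14", and adds: "Each participating individual will have no extra or additional outpatient study visits".
- The Risks section, part d (confidentiality), describes a second record: "Post-operative pain medication logs collected from patients in the outpatient setting at their first postoperative appointment will be given to the PI". It gives no day for that appointment and does not mention item 10.
- Section 7, under secondary outcome variables, has only a general rule that could apply: "T-tests or the nonparametric Mann-Whitney test will be used to compare normally and non-normally distributed data between the study arms". Nothing there deals with unequal time out of hospital or with patients who have no survey.

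**The concern.** The condition on the survey makes a patient's value depend on where the patient is on one day. For someone never discharged by day 14 this costs nothing, because there has been no outpatient use to record. For someone discharged and then readmitted, real opioid use at home goes unrecorded.

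Length of stay (item 5) and readmission within 30 days (item 8) are outcomes in their own right and may differ between arms. The Background (Section 3) itself cites evidence that epidural analgesia lengthens stay and raises complication rates in gynecologic cancer surgery. If that held here, the condition would remove more patients from the epidural arm, and the randomised comparison would become a comparison of patients selected by outcome. Item 10 is the only listed endpoint on opioid use after discharge, in a protocol that gives opioid reduction as part of its rationale.

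**Working it through.** The plan states no figure for this endpoint, so there is none to reproduce. The check sets the rules side by side and follows them through.

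**1. Who gets a value under item 10.**

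| Course up to day 14 | Any outpatient use possible? | Value under item 10? |
|---|---|---|
| Discharged, at home on day 14 | Yes | Yes |
| Discharged, readmitted, home again by day 14 | Yes | Yes |
| Discharged, readmitted, in hospital on day 14 | Yes | No |
| Never discharged by day 14 | No | No |

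The third row is the problem. The fourth is a reporting matter.

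**2. The condition does not follow the amount of outpatient time.** The days below are assumed for illustration and are not in the documents. Patient A is discharged on day 3, readmitted on day 10 and still in hospital on day 14: 10 - 3 = 7 days at home, no value. Patient B is discharged on day 3, readmitted on day 5 and home again on day 10: (5 - 3) + (14 - 10) = 6 days at home, with a value. The rule scores the patient with less time at home and omits the one with more.

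**3. Effect on an arm's mean.** Let p be the share of patients with some outpatient time who are unscored, m_s the mean of the scored and m_u the mean of the unscored. The full mean is (1 - p) × m_s + p × m_u, so

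full mean - scored mean = p × (m_u - m_s).

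The bias in the treatment difference comes from the difference between this term in the two arms. The documents give neither p nor m_u - m_s. If 5-10% of the 100 planned patients were in hospital on day 14 (an assumption), 5 to 10 patients would be unscored. That count includes any never discharged, so it is an upper limit for the third row at that assumed rate. With p between 0.05 and 0.10 in an arm, its mean would shift by 5-10% of the gap m_u - m_s. The sign of the gap is unknown.

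**4. Fit with the rest of the plan.** Section 7 states an intention-to-treat analysis and keeps the data of patients who stop taking part after surgery, unless they object in writing. Item 10 does the reverse for a readmitted patient who is still on study and willing to answer. Section 4b counts the inpatient stay and the 14 days after surgery as time on study, so a bedside contact on day 14 falls within it.

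**The case against.** Three arguments deserve weight.

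*The logs may fill the gap.* They could serve as a memory aid or source document for the call, and a readmitted patient's log might still be available. That is possible, but the plan does not say so. The logs are mentioned only in a passage about filing, and a patient readmitted before the first appointment may have handed in nothing.

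*Intention to treat is stated for testing the null hypothesis, not for item 10.* This is fair. The inconsistency is one of principle rather than a breach of an explicit rule for this endpoint.

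*Scoring readmitted patients has its own problem.* They have fewer days at home, so their totals could look low. This stands as a drawback, but it is not new: the plan already scores a patient readmitted and home again by day 14, and outpatient time varies with discharge day in any case. Reporting days at home makes it visible.

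A reader might also infer two stronger points that the documents do not support. The first is that the plan holds two competing definitions with different cut-offs. On that reading, with discharge on day 3 and an appointment between days 7 and 28 (all assumed), the log would cover 7 - 3 = 4 to 28 - 3 = 25 days against 14 - 3 = 11 for the call, a ratio of 4/11 = 0.36 to 25/11 = 2.27. But the confidentiality text names no endpoint, and Section 4a ends opioid collection on day 14. The day a log is handed in is not the day the endpoint closes. The second is that the arm with more readmissions loses its heaviest opioid users. Only status on day 14 matters, not any readmission, and nothing in the documents says how much readmitted patients take at home.

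**Conclusion.** The point holds in a limited form. Item 10 gives no value to a patient readmitted and in hospital on day 14, even for opioids already taken at home, and this selects on post-randomisation outcomes that are themselves endpoints. That conclusion rests on the text alone. The number of patients and the direction of bias cannot be derived from the documents; the 5 to 10 patients above depend on an assumed rate.

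The unexplained link between logs and survey is a smaller gap in wording. Severity is minor: one secondary endpoint is affected. The co-primary opioid total over 0-48 h comes from the medication administration record, and neither co-primary endpoint, the sample size nor the non-inferiority conclusion depends on item 10.

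**What to change.** Amend item 10 and align the sentence on logs in the Risks section:

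- Define the endpoint as opioids taken out of hospital from discharge to the end of postoperative day 14, in IV morphine equivalents.
- Delete the condition that the patient be an outpatient. Make the day-14 contact by phone, or in hospital for a readmitted patient.
- Name the log as the supporting record for that contact, and ignore entries after day 14.
- Report days at home with the total, and use per day at home as a sensitivity analysis.
- Report patients not discharged by day 14 separately by arm, as having no outpatient days.

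The cost is protocol and case report form wording plus a few bedside contacts. The call and the logs are already planned, and admission and discharge dates are needed anyway for length of stay and readmission. There are two drawbacks: readmitted patients contribute fewer days at home, and incomplete logs will have to be filled in from recall.
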